AIM 3: Determine the cost and cost-effectiveness of a peer mentorship intervention on disease self-management, disease activity, and HRQOL, in African American women with SLE. Hypothesis 3: A peer mentorship intervention in African American women with SLE will be cost effective at improving disease self-management, disease activity, and HRQOL, as measured by quality adjusted life years (QALYS), compared with the social support control group.

An exploratory aim will be to determine the role of mediators and moderators of a peer mentorship intervention on outcomes in African American women with SLE, with the hypotheses that disease self-management will act as a mediator and depression, trust, and social support will act as moderators of the relationship between the peer mentorship intervention and disease activity and HRQOL.

The peer mentoring approach is uniquely fitted to African Americans, and this intervention has the potential to lead to health improvements for African American women with SLE that have not been attainable with other interventions. This would significantly reduce disparities and have considerable public health impact.

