## Primary Outcomes for Aim 1 will include:

Quality of Life: The LUP-QOL incorporates the Medical Outcomes Study (MOS) Short Form 36 Health Survey (SF-36) and the Functional Assessment of Chronic Illness Therapy-Fatigue (FACIT-F), which are reliable and valid instruments that are frequently used in quality of life studies of persons with lupus.[120,121] Self-Management: The Patient Activation Measure (PAM)[122,123] assesses an individual's knowledge, skill, and confidence for managing their health and healthcare. Individuals who measure high on this assessment typically understand the importance of taking a pro-active role in managing their health and have the skills and confidence to do so.

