AIM 1: Determine the efficacy of a peer mentorship intervention in African American women with SLE on disease self-management and HRQOL. Analyses for Aim 1 will focus on estimation of efficacy as determined by: (a) change in quality of life; and (b) change in self-management. Estimates of effect sizes for outcome variables will be reported as point estimates (mean differences between pre-post measures. as appropriate) and interval estimates (95% CI) with two-sided p-vales denoting statistical significance to provide an indication of the presence of a clinically important treatment effect. [145,146] A p-value of 0.05 will be considered to be statistically significant. After studying the distributions of baseline characteristics. we will use a generalized linear mixed model regression model to determine if the intervention will produce a greater change in the main outcomes from baseline. This model will include time, treatment (along with their interaction), and covariates (including the amount of intervention received, demographic factors, medications, coping, depression, stress, anxiety, health literacy, trust, and social support) as fixed-effects. Using the amount of intervention, which is measured as an aggregate number of sessions completed or hours of interaction as a covariate would allow us to study the dose response. In the generalized linear mixed model (GLMM), we will use different link functions depending on the assumed distribution of the response variable. For binary outcomes, we will use logit link and for count outcomes we will use log link under a poisson or negative binomial distribution. For example, for the a given quality of life variable, HRQOL measured at baseline, month 3 and month 6, we will include intervention group, time, and time X intervention as the primary independent variables in the basic (unadjusted) model, and covariates that are not balanced at randomization (or a propensity score based on these covariates) will be added in the subsequent (adjusted) model to adjust for the possible confounding effect of these variables. Unadjusted and covariate-adjusted least squares means for each outcome variable will be compared at the primary time point (month 12) and at intermediate secondary time point (month 6) using appropriate model contrasts and the Tukey-Kramer adjustment for multiple comparisons for the secondary time points. These contrast comparisons, along with corresponding 95% CI, will provide estimates of the difference in outcome means (effect sizes) for the hypothesized comparisons.

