Secondary analyses of process measures: Important process measures will include recruitment, session attendance/dropout proportions and participant satisfaction. We will use 95% confidence intervals (CI) for proportions to estimate the proportion of participants who agree to participate out of the number who are initially approached, the proportion who are compliant with the treatment protocol, and the proportion who exit the study prematurely (drop out). In addition, frequency distributions describing the participants' reasons for noncompliance and discontinuation of study participation will be developed. We will also evaluate patient satisfaction with the peer mentoring intervention using a likert-type satisfaction scale and will determine the proportions (along with CI) within the categories. For continuous process measures (e.g. treatment credibility, treatment adherence, peer mentoring phone sessions and attrition), frequency distributions and the median and mean responses (with 95% CIs) will be obtained.

Exploratory analyses to determine the role of mediators and moderators on outcomes and obtain estimates of the effect of the intervention on mentors: Analysis for exploratory aims will focus on change scores over time for potential mediator and moderator variables related to identified unmet needs unique to African American women with SLE, including: (a) Anxiety; (b) Depression; (c) Stress; (d) Coping; (e) Health Literacy; (f) Trust; (g) Social Support; and (h) Patient centered care. Differences between baseline and post-baseline measurements will be tested with the Wald test in the GLMM model. As described for Aim 1, estimates of effect sizes for the outcome variables will be obtained via 95% confidence intervals (CI) to provide an indication of the presence of a clinically important treatment effect. Individual treatment change scores (pre-post) will be estimated via 95% CI (adjusting for clustering).[145,146] Since the intervention is designed to improve outcomes in mentees, we will not have power to test the efficacy of the intervention in the mentors, but will explore the effect of the intervention on the mentors using the same analytical methods.

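### The exploratory analysis tests change in the candidate mediator and moderator scales but specifies no treatment-by-moderator interaction and no indirect-effect model, so the stated mediation and moderation hypotheses go untested

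*Combined protocol and SAP*

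**What the plan says.** The exploratory aim, at the end of the specific aims in the Study Protocol section, gives its hypothesis as follows: "disease self-management will act as a mediator and depression, trust, and social support will act as moderators of the relationship". The link in question is from mentoring to two outcomes, disease activity and HRQOL.

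The matching method is the paragraph on exploratory analyses of mediators and moderators, under Overview of Statistical Analysis Plan. It states: "Analysis for exploratory aims will focus on change scores over time for potential mediator and moderator variables". The variables it names are "a) Anxiety; (b) Depression; (c) Stress; (d) Coping; (e) Health Literacy; (f) Trust; (g) Social Support; and (h) Patient centered care". The test is: "Differences between baseline and post-baseline measurements will be tested with the Wald test in the GLMM model". It then refers to Aim 1 for effect-size intervals.

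Elsewhere:
- The Aim 1 analysis lists its efficacy measures as "a) change in quality of life; and (b) change in self-management". Self-management is the PAM, a primary outcome for Aim 1.
- The Aim 1 model includes "medications, coping, depression, stress, anxiety, health literacy, trust, and social support) as fixed-effects". The only interaction it names is time by treatment.
- The Aim 2 responder model uses SLEDAI components as predictors.
- Section B4d plans analyses of differential effect by age and by number of comorbidities only.

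**The concern.** Moderation is a statement about how the treatment effect on an outcome varies with a third variable. Testing it needs a treatment-by-moderator term in the outcome model. Mediation needs a treatment-to-mediator path, a mediator-to-outcome path and an estimate of their combined (indirect) effect. The exploratory paragraph is presented as determining the role of mediators and moderators, yet the method it gives describes how the scales themselves change. Followed exactly, it leaves both hypotheses unanswered. The models that could answer them would then be chosen after the data are seen, with eight named scales and several outcomes to choose among.

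**Working it through.** **1. What each hypothesis needs, against what the plan supplies**

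| Needed | Supplied? |
|---|---|
| Treatment effect on PAM | Yes, as an Aim 1 outcome |
| PAM as predictor of disease activity or HRQOL | No |
| Indirect effect through PAM | No |
| Treatment × depression, trust, social support | No; main effects only (Aim 1 model) |
| Change in the eight scales | Yes (exploratory paragraph) |

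**2. Does the supplied test carry information on the hypotheses?** This was checked by simulation (1,500 replicates per setting, 240 participants, 1:1). The effect sizes are assumptions, since the documents give none for this aim. The plan was read generously, as comparing the arms on change in the scale.
- *Moderation.* True moderation was 0.35 per SD of a continuous baseline moderator, with no treatment effect on the moderator itself. The arm comparison of moderator change rejected 4% to 5% of the time (up to 6% with 300 participants), which is its type I level. The interaction test rejected 80% to 84% of the time.
- *Mediation.* The treatment effect on the mediator was 0.35 SD. When the mediator had no effect on the outcome, the treatment-to-mediator test alone still rejected about 77% of the time. A joint test of both paths rejected 4% to 5%. With a mediator-to-outcome path of 0.3, the joint test rejected 77% to 80%. A positive Aim 1 result on the PAM therefore cannot stand in for mediation.

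**3. The plan's only sizing figure.** The Power and Sample Size Justification gives 123 per group for 0.35 SD, two-sided 0.05, 80% power, correlation 0.6 and compound symmetry, including 20% for attrition.
- Variance of a change score: 2(1 − 0.6) = 0.8.
- 2 × (2.80/0.35)² × 0.8 = 102.5 per group; × 1.2 = 123.0. The figure is reproduced.
- B4c gives the same 123 with correlation 0.7 and AR(1), so both sets of inputs are carried into step 4. Nothing is stated for interactions or indirect effects.

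**4. What an interaction test could detect.** Completers: 300 × 0.8 = 240. For a standardised continuous moderator and 1:1 allocation, the detectable interaction at 80% power is 2.80 × √(v/(240 × 0.25)) = 2.80 × √(v/60), where v is the outcome variance in SD² units.
- Correlation 0.6, adjusted for baseline: v = 1 − 0.36 = 0.64, giving 0.29.
- Correlation 0.6, change score: v = 0.8, giving 0.32.
- AR(1) 0.7, two steps from baseline: v = 2(1 − 0.49) = 1.02, giving 0.37.
- AR(1) 0.7, three steps: v = 2(1 − 0.343) = 1.314, giving 0.41.

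With the moderator split 50/50 and v = 0.8:
- SE = √0.8 × √(4/120 + 4/120) = 0.231.
- Detectable interaction = 2.80 × 0.231 = 0.65 SD.
- Power for a 0.35 SD interaction is 33%.
- With 196 to 300 participants and a 30% to 50% split, the detectable size runs from 0.58 to 0.78 SD, and power for 0.35 SD from 24% to 40%.

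**The case against.** The best defence is that this is a labelled exploratory aim in an overview of the analysis plan, and that several stronger criticisms go too far.

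- A reader might infer that the plan leaves self-management out. It does not. The variable list opens with a word that makes it illustrative, it is tied to unmet needs, and the PAM is analysed under Aim 1. What is missing is the step from PAM to outcome. Adding PAM to a change-score test would not supply it.
- A reader might infer that the analysis shows only change over time. The reference to the GLMM and to Aim 1, whose model has a time-by-treatment term, supports reading it as between-arm differences in change. That is more informative, but it is still not moderation or mediation.
- A reader might infer that no candidate variable appears in an outcome model. Seven of the eight named scales are Aim 1 covariates; patient-centered care is the exception. They enter as main effects, and adjustment is not effect modification.
- A reader might infer that change scores will be used as moderators. The plan never says so; it treats them as quantities to estimate.
- The change analysis has its own purpose. The covariates section says several of these scales are there to show whether unmet needs are better met under mentoring.

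All of this stands and narrows the point. None of it supplies an interaction or an indirect effect.

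**Conclusion.** The point holds in this limited form: the stated method cannot answer either exploratory hypothesis, and no other part of the plan does so. No primary or secondary comparison, sample size or safety rule depends on it, so it should be fixed but is not critical.

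It would be too strong to conclude that the trial is well placed to test moderation once the terms are added. An interaction of 0.29 to 0.41 SD per SD of moderator is about as large as the whole planned effect of 0.35 SD. That range assumes 240 completers, a continuous outcome and moderator, and the plan's own correlation inputs. It ignores mentor clustering and the testing of three moderators on several outcomes, and it does not apply to the binary SLEDAI response in Aim 2. Dichotomising a moderator costs more power still. Interval estimates are the realistic product.

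**What to change.** - **Moderation:** add group × baseline depression, group × baseline trust and group × baseline social support to the month-12 LUP-QOL, SLAQ and SLEDAI models. Keep the moderators continuous and report interval estimates. Baseline values are needed because the intervention may change the later ones.
- **Mediation:** model month-6 PAM as mediator of the month-12 outcomes. Adjust for baseline PAM, the baseline outcome and measured baseline confounders of the mediator-outcome relation. Give bootstrap intervals for the indirect effect. State the assumption of no unmeasured mediator-outcome confounding, which randomisation does not secure.
- **Timing:** use month-3 PAM only once the schedules are reconciled. B4b and the Data Collection Process/Schedule include a month-3 assessment; the Data Collection Schedule in the human subjects section lists follow-up at 6 and 12 months only.
- **Labelling:** keep the pre-post changes as description, and state that power is limited, with the assumptions above.

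The cost is SAP wording and modest analysis time. The PAM and the baseline scales are already scheduled, so no new data are needed. The wording should be settled before outcome data are examined.

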#### Recruitment of Mentors

Potential peer mentors will first be invited from PALS pilot participants (mentees and mentors) (n=30), with the intention of retaining mentors to mentor multiple groups of mentees over the course of the study. It is expected that everyone would benefit from the use of experienced mentors, and using experienced mentors over time is also consistent with future real-world implementation. As needed (up to n=60, but approximately n=30 expected to be needed based on past research participation and interest), potential peer mentors who are considered competent in the management of their conditions will be identified by MUSC rheumatologists and subsequently trained by the PI. As part of the ongoing MUSC SLE database, patients are regularly flagged who providers deem competent enough to speak with the media on behalf of the patient population. We will mail out recruitment letters that will explain the study and provide participants a number to call if they are interested in participating. Participants who indicate interest in the study will be contacted by telephone to conduct a pre-screening assessment. If eligibility criteria are met, the screening/enrollment visit will be scheduled. As part of the mentor screening interview with the PI, psychosocial status will be assessed using the psychological scales of the Arthritis Impact Measurement Scales (AIMS), the Arthritis Helplessness Index (AHI), Wallston General Perceived Competence Scale, University of California at Los Angeles (UCLA) Loneliness Scale, Rosenberg Self-Esteem, Campbell Personal Competence Index. Carkhuff Communication and Discrimination Skills Inventories, and the Applied Knowledge Assessment (AKA) scale.[113] The PI will make a determination of competence, maturity, emotional stability, and verbal communication skills after overall assessment during the screening interview and training. Additional recruitment strategies will include the identification of local SLE support group members who have emerged as natural helpers, referrals from other rheumatologists and arthritis health professionals, and outreach to the local chapters of the Lupus and Arthritis Foundations by letter and telephone. Others have used these approaches successfully in multiple studies.

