**Data Collection Strategy** 

Data Collection Process/Schedule: Fourteen trained peer mentors will deliver the intervention in each wave and one full-time study coordinator (SC) will conduct screening, consent, enrollment procedures, and support group moderation. The primary method of data collection will be face to face interview. Mentees will be assessed at baseline, mid-intervention (3 months from baseline), immediately post-intervention (6 months from baseline), and 6 months post-intervention (12 months from baseline). Physical examination and laboratory evaluation will be achieved by in-person clinic visit when recent SLEDAI scores are not available in the database record of a given participant. Social support control participants will complete assessments on the same schedule as mentored participants. Given evidence that peer support may be just as beneficial to the supporters as it is to the person being supported, [118,119] mentors will be assessed on the same schedule as mentored and control participants, using the same tools.

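### The exploratory effect of mentoring on the mentors has no comparator and no defined baseline for returning mentors, so it should be reported as uncontrolled change

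*Combined protocol and SAP*

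**What the plan says.** The exploratory subsection of the Overview of Statistical Analysis Plan announces, in its title, estimates of the intervention's effect on mentors. It concedes that "we will not have power to test the efficacy of the intervention in the mentors", and then says it "will explore the effect of the intervention on the mentors using the same analytical methods".

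Those methods are set out in two places:

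- **Aim 1 analysis:** "This model will include time, treatment (along with their interaction), and covariates". The covariates include the amount of intervention received.
- **Exploratory subsection:** "Differences between baseline and post-baseline measurements will be tested with the Wald test in the GLMM model", and "Individual treatment change scores (pre-post) will be estimated via 95% CI (adjusting for clustering".

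On the mentors themselves:

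- The Randomization Procedure covers women recruited to the mentored or support-group conditions. Mentors are not allocated to anything. B4b (Study Overview) gives up to 60 mentors, with no division into arms.
- The Data Collection Strategy says "mentors will be assessed on the same schedule as mentored and control participants, using the same tools".
- Recruitment of Mentors sends the first invitations to pilot mentees and mentors (n=30), "with the intention of retaining mentors to mentor multiple groups of mentees over the course of the study". Women from the investigator's earlier studies may also serve as mentors (Study Population/Feasibility of Recruitment).
- Mentors are chosen after psychosocial screening and a judgement of competence, maturity and emotional stability.

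**The concern.** In the mentees, change since baseline in the support group is subtracted from change in the mentored group. Whatever both groups share then drops out: disease course, retesting, season, regression to the mean. Mentors have no such second group. If the mentees' methods are carried over, the treatment and treatment-by-time terms have nothing to contrast, and what is left is movement from baseline in one selected group. The plan calls this an effect of the intervention.

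Baseline is a second difficulty. A woman who took part in the pilot, or who mentored in an earlier wave, may already have gained or lost whatever mentoring brings. The plan does not say which of her measurements is the baseline or how earlier exposure is handled.

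At stake is a secondary message that is easy to publish: that mentoring helps, or harms, the mentor. The direction of error is not predictable. Regression to the mean in women picked for stability would look like worsening. Benefit gained before baseline would shrink the observed change. The mid-point rule removing mentors on a worsening trajectory would tilt later averages towards improvement if their later data are lost.

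**Working it through.** **Inputs from the documents.** Two-sided alpha is 0.05. Within-person correlation is at most 0.6 under compound symmetry, and the mentee effect size is 0.35 SD with 80% power (all from Power and Sample Size Justification). About 30 mentors are expected, with a ceiling of 60 (Recruitment of Mentors). Mentors per wave are 14 in the Data Collection Strategy but 20 in B4b. No sample size, power or precision figure is given for mentors.

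**Input assumed.** The drift unrelated to mentoring. The documents give no figure, so a range is shown.

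**Step 1: reproduce the plan's own figure, to confirm the correlation.**

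SD of change = √(2 × (1 − 0.6)) = 0.894.

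n per group = 2 × (0.894 × (1.960 + 0.842) / 0.35)² = 102.5, and 102.5 × 1.2 = 123.0.

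This matches the stated 123 per group, so 0.6 is a fair working value. B4c gives 0.7, which is used below as a sensitivity value.

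**Step 2: what each method estimates.**

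- Mentees: (mentored change) − (support-group change) = effect + drift − drift = effect.
- Mentors: change in one group = effect + drift.

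More mentors narrow the interval around effect + drift. They do not remove the drift.

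**Step 3: how often drift alone is significant.** Set the true effect on mentors to zero.

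SE = √(2(1 − 0.6)/n)

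P(p<0.05) = Φ(s/SE − 1.96) + Φ(−s/SE − 1.96), where s is the drift.

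For s = 0.2 SD:

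| Mentors | SE (SD) | 95% CI half-width (SD) | s/SE | P(p<0.05) |
|---|---|---|---|---|
| 14 | 0.239 | 0.47 | 0.84 | 13% |
| 30 | 0.163 | 0.32 | 1.22 | 23% |
| 60 | 0.115 | 0.23 | 1.73 | 41% |

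At 30 mentors, drifts of 0.1, 0.2 and 0.3 SD give 9%, 23% and 45%. With correlation 0.7 and drift 0.2 SD, the figures for 14, 30 and 60 mentors are 16%, 29% and 52%. The nominal rate is 5%. The normal approximation slightly overstates the rate at n=14.

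**Step 4: baseline.** The Data Collection Schedule places consent at the baseline visit, and Mentor Training places training at enrolment. A first baseline before training is therefore the natural reading, although the order is not stated. Nothing says whether a mentor who returns for another wave is measured afresh or keeps her first baseline.

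**The case against.** The plan calls the mentor work exploratory, says it lacks power, and promises no efficacy claim. That limits the importance of the point but does not answer it. Lack of power is a caveat about precision and suggests that more mentors would help, whereas Step 3 shows that more mentors make a spurious finding likelier. Elsewhere the protocol acknowledges that its pilot lacked a control group; the mentor analysis carries no such caveat.

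The plan also offers material for a comparison. The Aim 1 model includes amount of intervention to study dose response, mentors differ in load and log their hours, and support-group women are assessed at the same times with the same tools. A reader might therefore go too far and infer that the mentor model can contain nothing but visit, or that no information about an effect could ever be extracted. The documents do not support that. What stands is narrower: neither contrast is named for mentors, and both would be non-randomised and confounded, by what determines mentee load in one case and by selection for competence in the other.

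Two other stronger readings should be resisted:

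- That a returning mentor's baseline is known to follow earlier mentoring in this trial. No section says that returning mentors are re-baselined; the plan is silent.
- That a mentor's several waves will be counted as separate women, inflating false positives. The exploratory subsection says its intervals adjust for clustering, so the documents give no basis for assuming this.

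Finally, the drift values have no source in the documents. They illustrate the consequence and do not predict it.

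**Conclusion.** The point holds in limited form. With the stated methods and no named comparator, the mentor analysis yields uncontrolled pre-post change, and calling it an effect of the intervention goes beyond what the design supports. For returning or previously exposed mentors, the baseline also needs defining.

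The absence of a randomised contrast follows from the text alone and needs no assumption. The size depends on the unknown drift: at 0.2 SD and correlation 0.6, a significant result with no true effect arises in about 13% to 41% of trials across 14 to 60 mentors. The direction of bias cannot be stated in advance.

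The point is minor. It concerns one exploratory analysis and leaves the mentee randomisation, the primary contrast and Aims 1 to 3 untouched.

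**What to change.** In the exploratory subsection of the Overview of Statistical Analysis Plan, replace the closing sentence on mentors with wording such as:

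*Change in mentors will be described by visit, from one baseline per mentor taken before her first training in this trial, with 95% confidence intervals that account for repeated waves of the same mentor. No efficacy p-value will be given. Pilot participants and new mentors will be shown separately. Results will be reported as uncontrolled change and not as an effect of mentoring.*

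The subsection title should drop its reference to effect estimates in mentors. The sponsor should confirm that the first baseline precedes training, and should reconcile the two figures for mentors per wave.

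The cost is a wording change using measurements already planned. The downside is that no effect on mentors can be claimed, which the design does not support in any case.
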